3.3.5. Longitudinal Measures of Tidal Breathing Indices Using RIP

The ideal approach to obtaining longitudinal measure of tidal breathing would be to perform RIP at 1 year of age. However, there are several obstacles to acquiring these data. Tidal breathing patterns vary with state of consciousness and sleep state. Criteria for clinically determined quiet sleep have been validated in newborn infants, but not at 1 year of age. Thus we would have to document sleep state with electroencephalogram, greatly increasing the complexity of the study. There would also be challenges in being able to reliably time study visits with nap times at 1 year of age. These factors make it challenging to perform RIP at 1 year. However, a subset of infants in PROP will be undergoing IPFTs. The IPFT device is capable of measuring Tpef/Te via a mask with pneumotachometer. Previous studies have shown that Tpef/Te measured by RIP is equivalent to that of a mask,⁹⁹ and sedation with chloral hydrate does not affect this parameter.¹⁰⁰ Therefore we plan to obtain Tpef/Te in the cohort of infants undergoing IPFT at 1 year of age to assess longitudinal changes that may reflect changes in respiratory function.

3.3.6. **RIP and iPFT Data Quality**

The Infant PFT Core Laboratory at the University of North Carolina will serve as a consultant and service provider to the PROP.

We will incorporate several measures to ensure that respiratory function data will be obtained in a consistent fashion and be of research quality. Prior to initiation of the study, each of the PROP pulmonology site PIs with expertise in their respective respiratory assessment have refined the technique. We will develop a detailed manual of operations. In April 2011, we will have a training workshop with all of the site PIs and research coordinators to review the entire study protocol and provide hands on experience with the RIP equipment. During the validation phase of the study, each site's data will be reviewed to ensure adherence to procedure protocols.

Rochester, Buffalo, St. Louis, and Cincinnati have already been qualified by the CF Foundation in performing research quality iPFTs. The remaining iPFT site (UCSF) can receive qualification by sending 10 deidentified iPFTs for review by the CF Foundation Therapeutics Development Network Infant PFT Core Center. During the study, data from RIP, oximetry, and iPFT will be sent to the CF Foundation Therapeutics Development Network Infant PFT Core Center where they will be over-read by two blinded, independent overreaders. Only data that are certified as research quality by both overreaders will be used for analysis. The Core Center has extensive experience with these procedures, having successfully used them in the CF Foundation infant PFT study¹⁰¹ and the preschool PFT study; the Core Center is also performing iPFT data management for the NIH/CFF funded Infant Study of Inhaled Saline. The physician director is [name]. The lab will work with the DCC to establish and test the data transfer protocol and then schedule routine data transfers. The iPFT Core Laboratory will participate in evaluating test data quality from clinical sites and advise the DCC regarding the need for intervention or retraining

4. Statistical Considerations

4.1. Global Objectives

The global objectives of PROP are the investigation of hypotheses on the molecular mechanisms that contribute to respiratory disease risk of the premature newborn with the long-term goal of improving outcomes in the first year of life. More specifically the study design allows for the assessment of hypotheses of pathophysiological mechanisms and biomarkers that will characterize preterm infants and predict respiratory morbidity in several domains including medical resource utilization and respiratory symptoms over time and physiological and other measures at one year. PROP is a hypothesis generating multicenter study with myriad candidate predictors with the

longitudinal nature of the study allowing for the assessment of risk modification over time. Our development of the Statistical Considerations section will start with an examination of the primary outcome and main secondary outcomes. These sections will be followed by discussion of general power considerations, analytic approaches and more general statistical issues such as causal pathways, multiple comparisons, selection bias, and issues in generalization.

4.2. Primary Outcome

PROP has chosen an outcome that incorporates the elements currently considered as hallmarks of respiratory morbidity (Section 2.1). The primary outcome is dichotomous, and defined as "No substantial post-prematurity respiratory disease" or PRD. The definition of PRD for PROP requires that infants must have at least one morbidity element reported in at least 2 time frames (approximately 3 month intervals). Survey items selected for the determination of the primary outcome will be focused on four domains, with any positive response to any element identifying morbidity: respiratory medications; hospitalizations for cardiopulmonary cause; respiratory symptoms; home technology dependence; and death.

Follow up data from recently published randomized controlled trials and observational studies in similar but not identical populations of very preterm infants suggest that the incidence of this primary outcome will be at least 30% and possibly as high as 60%.³²⁻³⁵

4.2.1. **Predictors of Outcome**

The primary focus of PROP is on the delineation of early and later biomarkers during the NICU stay that predict *respiratory morbidity post discharge through 1 year of age*. The later predictive biomarkers will include various physiologic respiratory assessments described in section 3.2. Some infants will be ineligible for any of these tests, e.g. those on mechanical ventilation at 36 and 40 weeks PMA. The values for these ineligible infants for these examinations will generally be assumed to have a failure in the respective test.

4.3. Secondary Outcomes

4.3.1. Mortality

Mortality as an outcome will be described as a dichotomous outcome as well as the time to death. Logistic regression will be used to predict mortality using covariates from the NICU period and Cox Regression will be used in examining time to death, also using the covariates from the NICU period.

4.3.2. **Physical Examination Score**

Physical Examination Score will be a composite of the weighted results of a 12 month battery of physical measurements including weight, Z-score, respiratory rate (awake, w/ RIP), SpO2 in RA, retractions, thoraco-abdominal movement, accessory muscle use, wheeze, wheeze character, crackles, digital clubbing , done at one year visit on all eligible infants.

4.3.3. Respiratory Morbidity Severity Score

The respiratory morbidity severity score will be used to quantify the level of morbidity in each of the domains of resource utilization and symptoms. The outcome would be based on a scoring system involving the elements already described in the four domains of the primary composite outcome (Section 1.0).

4.3.4. Refined Assessment of the Primary Outcome PRD

In secondary analyses, PRD will be defined in various ways to assess the sensitivity of the outcome to the chosen definition described in Section 4.2. These variations will include but not be limited to:

- The predictive ability of specific biologic, physiologic and clinical data obtained during the initial hospitalization will be compared to the predictive ability of the currently available definitions of BPD: (i) use of supplemental oxygen at 36 weeks PMA; (ii) NIH consensus definition that distinguishes between mild, moderate and severe BPD; (iii) "physiologic" definition.
- Repeated measures of morbidity at each visit defined as a binary indicator of at least one element out of four morbidity elements. Though different from what is measured in the primary outcome, this approach defines persistence of respiratory disease without specifying a particular PRD element or pattern and will utilize all complete surveys at any time point, and thus can be more robust when there is missing data (e.g. 3 month survey not done).
- Changing the frequency requirement of 2 time intervals to 3 time intervals, to create an ordinal outcome such as mild (< 2 time intervals), moderate (only 2 intervals) and severe (3 or more time intervals).
- Weighting the various components, such as hospitalizations having more weight than medications alone.

4.4. Power Considerations

Since the sample size of 750 participants was established by the RFA, discussion of power will be in the context of this fixed sample size for the primary outcome. We have made assumptions concerning loss to follow-up due to death and non illness related departures. As will be seen, the sample size is adequate to provide appropriate power for all of the examples presented below, which should account for reasonable departures from our assumptions, without losses of sensitivity to detect meaningful differences.

4.4.1. **Primary Outcome**

Our primary outcome PRD is binary and we will use logistic regression models to test the correlation between a biomarker and the outcome. With current sample size, we consider a range of PRD rates from 30% to 50%, allowing us to conceive a possible range of power. We also let the odds ratios (OR) for the change of one standard deviation in the biomarker vary from 1.2 (small effect) to 1.6 (moderate effect). Assuming no measurement errors and no correlation between the biomarker and other covariates, Figure 4.4.1 shows the power to detect various odds ratios for the possible outcome with PRD rates of 30%, 40% and 50% at $\alpha = 0.05$ using a two-tailed test.

Because the power is the same for any two PRD rates symmetric around 50% (e.g., 40% and 60%), we only show the power for PRD rates up to 50%. Power increases as the PRD rate and the minimum detectable odds ratio increase. For a PRD rate of 40%, given a sample size of 750 and a conservative missing rate of 10% (5% due to late deaths and 5% due to loss to follow up), we will have sufficient power (>80%) to detect a significant biomarker-PRD association at OR of 1.25 or higher for one S.D. increase in the biomarker.

Odds Ratio for One SD Change of the Biomarker Variable

Figure 4.4.1: Power of detecting a significant association between a biomarker and the binary outcomes for various odds ratios at a significance level of α =0.05 assuming a missing rate of 10%.

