3.3. Assessments During Follow-up to 1 Year Corrected Age

Research staff at the clinical PROP centers will obtain follow-up data from the infant's primary caregiver after the infant has been discharged from the hospital. This will require a significant investment of time and energy and is essential to characterize the respiratory status of study participants during the first year of life. We aim to achieve a very high retention rate of at least 90% and ideally > 95% to minimize ascertainment bias.

3.3.1. Data Collection at Months 3, 6, 9 and 12

At age 3, 6, 9, and 12 months corrected age (+ 1 month corrected age), the research staff at the clinical centers will contact the family to schedule and conduct an interview with the primary caregiver about the infant's health status. Contact information will be verified and revised as needed. A focused questionnaire will be administered over the telephone or in person at 3, 6, 9 and 12 months corrected age by the research staff to gather detailed data about hospitalizations for cardiopulmonary causes as well as for other medical reasons, respiratory medication use, respiratory symptoms and home technology dependence. For further details please refer to section 2.1

Medication used during the previous 3 months will be reported by parents to the site staff by listing them in advance of each follow-up call and reading them to the interviewer or by reading the labels to the interviewer at the time of the encounter. Exposure to environmental risk factors (young siblings, smoking, kerosene heater, pets) will also be recorded. Lastly, we will administer a symptom survey for gastroesophageal reflux disease (GERD) that was developed and validated for infants and children < 18 months by Orenstein and colleagues.⁷⁸ The 12-item questionnaire assesses symptoms associated with reflux over the past week.

3.3.2. Physical Examination at Month 12

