4.4.2. Secondary Outcomes

There will be several outcomes and subgroup analyses, including outcomes that are individual components of the broad domains already described. We consider the general question of power with a cohort of 750 as well as smaller sample sizes, by examining the relevant parameters for sample size/power assessment for a hypothesis test of a correlation between a continuous prognostic biomarker and a dichotomous or continuous one year outcome of interest using a logistic or linear regression.

For scenarios where the outcome is determined to be binary (e.g. respiratory re-hospitalization or not), we will use logistic regression to test the correlation between a biomarker and the binary outcome. If we consider a range of the outcome event rates from 30% to 50%^{1, 32, 102} and examine the same missing rates as above, we will have the same power estimate as shown in Figure 4.4.1. Please note that respiratory re-hospitalization takes discrete non-negative ordinal values and will be analyzed using the proportional-odds (or ordinal logistic) regression models to test the correlation between a biomarker and the outcome. Such models allow unequal spaced differences among ordinal scales and yet estimate the common effect of predictors on the increasing scale of the outcome. Our power estimate based on the dichotomized variable is conservative and our planned proportional odds models generally have higher power than the logistic regression for a dichotomized outcome.¹⁰³ For other secondary outcomes that might be described as approximately continuous, we can assess the value of a biomarker as the

proportion of the outcome variance explained by the biomarker (R²). One outcome that will be considered is a one year physical exam score.

Figure 4.4.2 shows the power to detect a significant association between a biomarker and a continuous outcome. For example, for the sample size of 750 and R² of 0.5% to 2% (equivalent effect sizes of 0.071 SD to 0.143 SD, which are generally considered as small effects) the power was estimated assuming conservative missing rates of 5% and 10% (as in Section 4.4.1 above) using $\alpha = 0.05$.^{104, 105} Clearly for a continuous outcome, the PROP cohort will provide sufficient power to detect significance for even a small effect size.

Figure 4.4.2: Power of detecting a significant association between a biomarker and a continuous outcome for various effect size at a significance level of α =0.05.

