Since the analysis will be adjusted for covariates including gender, birth weight, and gestational age at birth, the sensitivity of the analysis may be affected by the actual correlation between the biomarker and the covariate and the effect of the covariate. If multiple independent biomarkers can jointly explain the outcome, we are likely to have higher power to detect at least one of these biomarkers.

We may investigate the biomarker-outcome association analysis in a certain gestational age group. In the power assessment to follow, since the distribution of the numbers of infants born in 23-24, 25, 26, 27, and 28 weeks is close to uniform from sites' preliminary data, we assume there are 150 infants in each group, for which the power for detecting a significant association between biomarker and continuous outcome at $\alpha = 0.05$ is shown in Figure 4.4.3. Also in the same figure, we labeled the x-axis with the corresponding odds ratios assuming the power to detect the association between a biomarker and dichotomized outcome with an event rate of 40%. Given the subgroup sample size of 150, we will have 80% power to detect a significant association for an effect size of at least 0.24 (generally considered a small effect size) for a continuous outcome or an odds ratio of 1.64 or larger (a moderate OR) for a dichotomized outcome. Note that the minimum detectable effect size (Figure 4.4.3) required for subgroup analysis is more than twice that required using the full cohort (Figure 4.4.1, 4.4.2).

Figure 4.4.3: Power of detecting a significant association between a biomarker and the dichotomized/continuous outcome for various odds ratio/effect size (top/bottom x labels) in a subgroup at a significance level of α =0.05 assuming a missing rate of 10%.

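### Sections 4.4 and 4.4.2 claim adequate power for every example and for even a small effect, but at the lower end of the protocol's own ranges power is 45% to 76%

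*Protocol*

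**What the plan says.** Section 4.4 takes the sample size as given ("Since the sample size of 750 participants was established by the RFA"). It then states that "the sample size is adequate to provide appropriate power for all of the examples presented below", and adds "which should account for reasonable departures from our assumptions, without losses of sensitivity to detect meaningful differences".

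The examples that follow are:

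- **Section 4.4.1, primary outcome.** PRD rates of 30% to 50% and odds ratios of 1.2 to 1.6 per SD of the biomarker, two-sided alpha 0.05, 10% missing (5% late deaths, 5% loss to follow-up). The only power figure given in the text is more than 80% for an odds ratio of 1.25 or higher at a PRD rate of 40%. The section describes that level of power as sufficient. The calculation is made "Assuming no measurement errors and no correlation between the biomarker and other covariates".
- **Section 4.4.2, continuous outcomes.** R² of 0.5% to 2%, expressed as 0.071 to 0.143 SD and described as small, with 5% and 10% missing. The conclusion is: "Clearly for a continuous outcome, the PROP cohort will provide sufficient power to detect significance for even a small effect size".
- **Section 4.4.2, adjustment.** A later paragraph begins "Since the analysis will be adjusted for covariates including gender, birth weight, and gestational age at birth" and warns that correlation between biomarker and covariates may affect sensitivity. It gives no figure.

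**The concern.** Section 4.4 makes a general claim about a grid of event rates and effect sizes, but the text gives a power figure for only one point of the primary-outcome grid. That point lies close to the 80% threshold. Points with a smaller effect or a lower event rate must then fall below it, and several of those are among the protocol's own examples. The continuous-outcome sentence is more exposed, because it names an R² range starting at 0.5% and at once declares power sufficient for small effects.

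The study screens many candidate biomarkers. A reader who takes these sentences at face value would overestimate the chance that a weak but real marker is detected.

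**Working it through.** **Inputs, all from the protocol.** N = 750; alpha 0.05 two-sided; 10% missing, so n = 675 (5% missing gives n = 712); PRD rate p = 30%, 40%, 50%; odds ratio per SD from 1.2; R² from 0.5% to 2%. The benchmark is 80%, as in 4.4.1.

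**Binary outcome.** Logistic regression on a standardised continuous predictor:

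power = Φ( √(n·p·(1−p)) · ln OR − 1.96 )

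The same formula, with n divided by 0.9, returns five of the six sample sizes in Table 4.8.1 (253, 222, 130, 213, 124), so it appears to be the protocol's own method.

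*Reproducing the stated figure* (OR 1.25, p = 40%, n = 675): √(675 × 0.24) = 12.73; 12.73 × 0.2231 = 2.840; 2.840 − 1.960 = 0.880; Φ(0.880) = 81.1%. Simulation gave 80.9%, and a Wald version with information taken under the alternative gave 79.7%. The stated >80% stands.

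*The other points of the protocol's grid, n = 675:*

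| PRD rate | √(n·p·(1−p)) | Power, OR 1.2 | Power, OR 1.25 | OR detectable at 80% |
|---|---|---|---|---|
| 30% | 11.91 | 58.3% | 75.7% | 1.265 |
| 40% | 12.73 | 64.1% | 81.1% | 1.246 |
| 50% | 12.99 | 65.9% | 82.6% | 1.241 |

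The last column is exp(2.802 / √(n·p·(1−p))), where 2.802 = 1.960 + 0.842. For OR 1.25 at 30%, the Wald version gave 74.6% and simulation 73.6%.

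With all 750 infants analysed, OR 1.2 still has only 62.9% to 70.4% power, and OR 1.25 at 30% only just reaches 80% (79.96%).

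**Continuous outcome.** F test for one predictor, with noncentrality λ = n·R²/(1−R²) and degrees of freedom 1 and n−2.

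The protocol's effect-size conversion reproduces: √(0.005/0.995) = 0.071 and √(0.02/0.98) = 0.143. For R² = 0.5% and n = 675, λ = 675 × 0.005/0.995 = 3.39.

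| R² | n = 675 | n = 712 | n = 750 |
|---|---|---|---|
| 0.5% | 45.2% | 47.2% | 49.2% |
| 1% | 74.1% | 76.4% | 78.5% |
| 2% | 96.0% | 96.8% | 97.4% |

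Simulation at R² = 0.5% gave 45.6% (n = 675) and 47.0% (n = 712). At n = 675, 80% power needs R² of about 1.15% (0.108 SD). At R² = 0.5% it needs about 1,564 infants analysed.

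**Sensitivity to covariate adjustment (assumed values; the protocol gives none).** If the covariates explain a share R²c of the biomarker's variance, n is multiplied by (1 − R²c). At p = 40% and n = 675, R²c = 0.1 gives a detectable OR of exp(2.802/(12.73 × √0.9)) = 1.26, and R²c = 0.3 gives exp(2.802/(12.73 × √0.7)) = 1.30.

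**The case against.** The strongest defence is that no specific power figure for the primary outcome is wrong. The claim at OR 1.25 is conditional on a 40% PRD rate and reproduces. The ranges of event rate and odds ratio can be read as plotting grids, and power curves normally include values below 80%. Figures 4.4.1 and 4.4.2 are not shown in the text available and may display the low values openly. The subgroup examples in 4.4.2 (0.24 SD and OR 1.64) come out at 79% and 80% with 135 analysed.

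Much of this stands, and it confines the point to two general statements. It does not rescue 4.4.2, which names R² of 0.5% to 2% as its example and then concludes that power is sufficient. If the figures do show about 45%, the sentence contradicts them.

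Three stronger readings are tempting, and the documents do not support them:

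- **That expected missingness is really 15%.** A reader might add 5% deaths to the 10% loss allowed by the retention floor in section 3.3. That section does not say deaths lie outside its 90%, section 4.7.3 expects missing outcome data from deaths and attrition together to be at or below 10%, and section 2.1 counts late cardio-respiratory deaths as PRD. The effect would be small in any case: n of about 637 gives 78.8% instead of 81.1% at OR 1.25 and a 40% rate.
- **That adjustment is known to cost a given amount of power.** The direction follows from the planned adjustment, but the protocol gives no biomarker–covariate correlation. It declares the zero-correlation assumption in 4.4.1 and cautions about it in 4.4.2.
- **That null results will be reported as absence of association.** Section 4.6.4 calls the study hypothesis generating and uses significance to flag candidates for confirmation; section 4.6.2 promises confidence intervals. The documents plan no such inference.

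**Conclusion.** The two general statements are wrong as written. At 10% missing and with no covariate adjustment, power is about 45% for R² of 0.5%, 74% for R² of 1%, 58% to 66% for OR 1.2 across PRD rates of 30% to 50%, and about 76% for OR 1.25 at a 30% rate. These results use only protocol inputs and standard formulas. R² of 0.5% and OR 1.2 stay well under 80% even with no loss at all.

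The claim that reasonable departures are absorbed also fails on the protocol's own terms: moving the PRD rate from 40% to 30%, the lower end of its expected incidence, takes OR 1.25 below 80%.

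A reader might infer that the primary outcome is underpowered as planned. That does not follow. The specific claim at OR 1.25 and 40% is right, power at OR 1.25 stays above 80% from 40% to 60%, and at 30% the detectable odds ratio moves only to about 1.27. This is an overstated description of a fixed design.

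**What to change.** In section 4.4, delete the statement that "the sample size is adequate to provide appropriate power for all of the examples presented below" together with the clause on absorbing departures. In 4.4.2, delete the sentence "Clearly for a continuous outcome, the PROP cohort will provide sufficient power to detect significance for even a small effect size". Replace them with text to this effect:

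- Unadjusted and with 10% missing, there is 80% power for an odds ratio per SD of at least about 1.25 at PRD rates of 40% to 50%, and about 1.27 at 30%.
- For continuous outcomes there is 80% power for R² of at least about 1.2%.
- OR 1.2 and R² of 0.5% to 1% are below 80%.
- The figures assume no correlation between biomarker and covariates, so detectable effects will be larger after the planned adjustment wherever such correlation exists.

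A covariate or 15%-missing scenario should appear only as a labelled sensitivity range. For example, at a 40% PRD rate and n = 675, an assumed R² of 0.1 to 0.3 between biomarker and covariates gives a detectable odds ratio of about 1.26 to 1.30.

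The cost is a few sentences and slightly less favourable stated figures. Enrolment, procedures and analyses do not change.

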2.1. Primary Outcome: Post-prematurity Respiratory Disease

The primary goal of the PROP studies (single center and multicenter protocols) is to identify biomarkers (biochemical, physiological and genetic) and clinical variables that are associated with and thus potentially predictive of pulmonary status in preterm infants up to 1 year corrected age. An objective and validated measure of pulmonary outcome at 1 year does not currently exist. Some promising measures are in development but not yet ready for use in a multi-center large clinical study. For example, reduced alveolar number is a key pathologic feature of BPD .²¹ Physiologically, this is reflected in decreased diffusion capacity of the lung to carbon monoxide (DLCO), and infants with BPD have lower DLCO compared to healthy full term controls.²² However, measurement of infant DLCO in a multi-center study is not feasible in PROP because of the lack of standardized equipment, the need for C¹⁸O instead of standard CO, and the need for a mass spectrometer to measure CO instead of a standard infrared sensor.²³

Moreover, the PROP investigators firmly believe that the burden of chronic respiratory illness on the infants and their families is of utmost importance. Therefore, we propose a composite primary outcome of morbidity that is based on serial parental reports of respiratory symptoms, medications, hospitalizations and dependence on technology during the first year of life.

Data collection for the outcome assessment will be based on interviews conducted with the infant's main caregiver at 3, 6, 9 and 12 months corrected age. The time frame for data collection is based on questions "since last contact." Numerous epidemiological studies of asthma have used parental or self report of symptoms, physician-diagnosed asthma and allergies, or the use of medications (which may abrogate symptoms) as critical outcomes.^{16, 24-26} Recent studies have most commonly employed the International Study of Asthma and Allergies in Childhood (ISAAC) questionnaire.²⁷ These studies have collected data regarding 1 year old children, although not children before one year of age. The questionnaire to be utilized in PROP has been modified from the Tucson Children's Respiratory Study (CRS)^{20, 28-31} and the Breathing Outcomes Study. The latter is an ancillary study for the NICHD Neonatal Research Network (NRN) Surfactant Positive Airway Pressure and Pulse Oximetry Trial (SUPPORT).

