Four centers have proposed projects that involve tracheal aspirate assays or genotyping as part of either their single center or multi-center proposal. Four centers have proposed studies of urinary biomarkers. The rapid changes in sequencing technology will permit acquisition of significantly more sequence data at less cost within the next 3-4 years; the DNA repository is therefore viewed as a resource for PROP investigators to develop additional proposals in later years that utilize the power of this large number of samples and extensive sequencing capacity to address more specific mechanistic/genetic questions. Thus, expected use of the repositories is substantial and the biospecimen along with extensive clinical data provide a novel resource for PROP as well as future investigators. In addition, collection of these three types of biospecimen is relatively straightforward and non-invasive without a major impact on PROP personnel, families, or funding.

All centers will obtain samples of tracheal aspirate, urine and saliva (for DNA extraction) from enrolled infants. In addition, saliva will be obtained from mothers, and fathers when possible, of enrolled infants. Tracheal aspirate and urine samples will be archived in investigator-led laboratories at UCSF and Vanderbilt, respectively. The Center for Human Genetics Research (http://chgr.mc.vanderbilt.edu) at Vanderbilt University will serve as the repository for the DNA specimens. The following samples will be collected from study participants using standardized methods:

- a. Saliva for DNA extraction will be collected preferably during the first week or alternatively later during hospitalization or at the 1-year follow-up visit
- b. Tracheal aspirate samples will be obtained during routine suctioning of intubated patients for clinical purpose
- c. Urine samples will be collected from cotton balls that are placed in the diaper
- d. Tracheal aspirates and urine samples will be collected on the following schedule:
 - o 2 samples at 2-4 days in the first week after enrollment;
 - o 1 sample 7 days later;
 - o 1 sample at 28 days postnatal

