The participant must be informed that he/she will be notified of any significant **changes** in the protocol that might affect their willingness to continue in the study

The consent process may differ somewhat by clinical center according to local IRB guidelines and single center study procedures. The informed consent document will be structured such that it enables potential participants to indicate which aspects of study they may not be willing to engage in.

5.1.6. **Consent for Genetic Testing and DNA Storage**

A separate section and signature page will be required for consent to collect a saliva sample for genetic testing and storage of DNA. A parent may refuse to sign the separate consent for use

of DNA without consequence to study eligibility. Specimens will be stored at The Center for Human Genetics Research at Vanderbilt University. At a later date, the specimens will be submitted to the NHLBI BioLINCC Repository (https://biolincc.nhlbi.nih.gov/home/).

A separate section for indicating the choice to contribute other biospecimens specific to the studies at each site, which will include the collection, for the PROP biorepositories, of 4 tracheal aspirate samples (if the infant is intubated) and 4 urine samples at pre-specified postnatal ages.

Participants will be informed that DNA and other biological samples may be used for many types of genetic and biomarker analyses, but that the confidentiality of this information will be ensured by (1) data security measures, at the participating sites and DCC, and (2) at the point that their clinical information is combined with biological data (e.g., genetic studies) where these datasets will be de-identified. Information generated from these samples will not be reported to study participants. Paternity will not be determined.

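### The >80% power at OR 1.25 in Protocol Section 4.4.1 is offered for any biomarker, but it holds only for predictors available in nearly all infants, which tracheal-aspirate markers are not designed to be

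*Protocol*

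**What the plan says.** Section 2.1 sets the primary goal as to "identify biomarkers (biochemical, physiological and genetic) and clinical variables" associated with respiratory status up to 1 year corrected age. Biochemical and genetic markers are therefore part of the main question.

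Section 4.4.1 gives the power for the binary primary outcome, PRD. It works over PRD rates of 30% to 50% at two-sided alpha 0.05, and assumes no measurement error and no correlation between the marker and other covariates. Its headline, for a 40% rate, is "sufficient power (>80%) to detect a significant biomarker-PRD association at OR of 1.25 or higher for one S.D. increase" in the marker. The claim is made "given a sample size of 750 and a conservative missing rate of 10% (5% due to late deaths and 5% due to loss to follow", and no other loss is allowed for.

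Other sections determine who will have a marker value:

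- Section 3.1.3: "Tracheal aspirate samples will be obtained during routine suctioning of intubated patients for clinical purpose". Samples are scheduled in the first week after enrolment, 7 days later, and at 28 days. Urine is collected from the diaper, and saliva for DNA may be taken as late as the 1-year visit.
- Section 5.1.6: "A parent may refuse to sign the separate consent for use" of DNA and remain eligible. Contribution of other biospecimens is a separate choice, and aspirates are again conditional on intubation.

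**The concern.** A regression of PRD on a marker uses infants who have both. Section 4.4.1 deducts for a missing outcome and so assumes, without listing it among its assumptions, that every infant with an outcome also has the marker. For aspirate markers the design rules this out for any infant not intubated at a sampling time.

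No other section makes the allowance. The rule in Section 4.2.1 that treats ineligible infants as test failures covers the respiratory assessments only. Section 4.7.3 deals with missing outcome and one-year data. The subgroup power in Section 4.4.2 is for gestational-age strata of 150. By contrast, Section 4.8.2 does discount the infant lung-function sample for consent and test failure.

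At stake is how a null result is read. Someone relying on Section 4.4.1 would take a negative finding for an aspirate marker as evidence from a study able to see OR 1.25, when the number sampled may not support that.

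**Working it through.** **Inputs from Section 4.4.1.** N = 750; 10% loss; PRD rate p = 0.40; OR = 1.25 per SD, so ln OR = 0.2231; two-sided alpha 0.05 (z = 1.960); 80% power (z = 0.842). The share of infants with a given specimen is not in the protocol and is varied below as an assumption.

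**Formula.** For logistic regression on one standardised continuous covariate:

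- power = Φ(√(n·p(1−p))·ln OR − 1.960)
- required n = (1.960 + 0.842)² / [p(1−p)(ln OR)²]
- OR detectable with 80% power = exp(2.802 / √(n·p(1−p)))

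**Reproducing the printed figure.** n = 750 × 0.90 = 675. √(675 × 0.24) = 12.73; 12.73 × 0.2231 = 2.840; 2.840 − 1.960 = 0.880; Φ(0.880) = 81.1%. The claim of more than 80% is reproduced.

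The formula appears to be the protocol's own. With n/0.9 it returns five of the six entries of Table 4.8.1 (253, 222, 130, 213, 124), and at n = 135 (150 less 10%) it gives 80.4% power for the OR of 1.64 quoted in Section 4.4.2.

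**Margin.** Required n = 7.849 / (0.24 × 0.04979) = 656.8, so 657. As a share of 675 this is 97.3%. The statement fails once more than about 2.7% of infants with an outcome lack the marker.

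**Effect of marker availability** (p = 0.40, n = 675 × share):

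| Share with marker (assumed) | n | Power at OR 1.25 | OR detectable at 80% |
|---|---|---|---|
| 100% | 675 | 81.1% | 1.246 |
| 95% | 641 | 79.1% | 1.253 |
| 90% | 608 | 76.9% | 1.261 |
| 80% | 540 | 71.9% | 1.279 |
| 70% | 473 | 66.1% | 1.301 |
| 50% | 338 | 51.9% | 1.365 |
| 30% | 203 | 34.3% | 1.495 |

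**Sensitivity.**

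- *Late deaths.* Section 2.1 counts late cardio-respiratory deaths as PRD, so part of the 5% is not missing. As an upper bound, if all late deaths count, n = 750 × 0.95 = 712.5, power is about 83%, and the break-even share is 656.8 / 712.5 = 92.2%. At 70% and 50% availability (n = 499 and 356), power is Φ(0.481) = 68% and Φ(0.103) = 54%.
- *Event rate.* Infants with a specimen may have a different PRD rate. At 50%, the most favourable, required n is 630.5, or 93.4% of 675; power is 79% at 90% availability and 54% at 50%.
- *Formula.* A Wald calculation with expected information gives 79.7% at the full 675, so the exact break-even depends on the method.

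**The case against.** A reader might infer that the 81% is miscalculated. It is not: it reproduces, and it is valid for a marker measured in essentially every infant.

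A reader might also infer that DNA markers lack the printed power. The protocol does not support that. It gives no consent rate and allows saliva collection up to the 1-year visit. At 95% uptake power is 79.1%, a trivial loss; above about 97% the statement stands. Nor does the intubation limit apply to urine, which is also a biochemical source.

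The break-even should not be pressed to the decimal. It lies between about 92% and 97% depending on how late deaths and the event rate are treated.

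Figures for smaller samples are already in the protocol: OR 1.64 for a subgroup of 150 (Section 4.4.2), and OR 1.5 at an effective 200 with a 40% rate (Section 4.8.1), close to the 30% row above. A careful reader could interpolate, but those figures are for gestational-age strata and for phase angle against hospitalization, and nothing links them to specimen markers.

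Finally, the sample size was fixed by the funding announcement, the study is described as hypothesis generating, and confidence intervals and missing-data patterns are to be reported. This is a good reason not to ask for more infants, and it softens the consequence. It does not justify a power statement wider than the calculation behind it.

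**Conclusion.** The point holds as one of scope. The printed power applies to predictors available in nearly all infants with an outcome: about 97% of 675, or as low as about 92% if all late deaths count as PRD.

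For tracheal-aspirate markers it does not apply unless nearly all infants are intubated and sampled, because Sections 3.1.3 and 5.1.6 confine aspirates to intubated infants. For DNA and other separately consented specimens the conclusion is conditional on an uptake that the protocol does not state.

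The size of the shortfall cannot be fixed from the document. The main figures (77%, 66% and 52% power at 90%, 70% and 50% availability) rest on those assumed shares and on a 40% PRD rate among infants with the specimen.

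**What to change.** In Section 4.4.1:

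1. Limit the OR 1.25 / more than 80% statement to predictors available in essentially all infants with an outcome.
2. Add a short table of detectable odds ratios for aspirate markers, and conditionally for DNA, over a stated availability range. At PRD 40% with n = 675 × availability these are 1.26 at 90%, 1.30 at 70%, 1.37 at 50% and about 1.50 at 30%. Replace the assumed shares with expected intubation and consent figures if the sites can supply them.
3. State that results for aspirate markers apply to infants intubated at the sampling time.

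The cost is wording and one table, with no added infants or procedures. The downside is a less favourable stated detectable odds ratio for those markers.
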